## **12. Pharmaceutical Information**

### **12.1 Investigational Agents**

There are no investigational agents involved in this study.

### **12.2 Commercial Agents Product description:**

Cetuximab is a commercially available agent..

Preparation: Cetuximab® (cetuximab) is supplied at a concentration of 2 mg/mL as a 100 mg/50 mL, single-use vial or as a 200 mg/100 mL, single-use vial as a sterile, preservative- free, injectable liquid. It should be prepared as for standard preparation as per the package insert. Store vials under refrigeration at 2° C to 8° C (36° F to 46° F). Do not freeze. Increased particulate formation may occur at temperatures at or below 0° C. This product contains no preservatives. Preparations of cetuximab in infusion containers are chemically and physically stable for up to 12 hours at 2° C to 8° C (36° F to 46° F) and up to 8 hours at controlled room temperature (20° C to 25° C; 68° F to 77° F). Discard any remaining solution in the infusion container after 8 hours at controlled room temperature or after 12 hours at 2° C to 8° C. Discard any unused portion of the vial.

Route of administration:

Premedicate with an H1 antagonist (eg, 50 mg of diphenhydramine) intravenously 30–60 minutes prior to the first dose; premedication should be administered for subsequent Cetuximab doses based upon clinical judgment and presence/severity of prior infusion reactions.

Administer 400 mg/m^2 initial dose as a 120-minute intravenous infusion followed by 250 mg/m^2 weekly infused over 60 minutes. Reduce the infusion rate by 50% for NCI CTCAE Grade 1 or 2 infusion reactions and non-serious NCI CTCAE Grades 3–4 infusion reactions. Permanently discontinue for serious infusion reactions. Withhold infusion for severe, persistent acneform rash. Reduce dose for recurrent, severe rash.

Expected toxicities: The most common adverse reactions (incidence  $\geq 25\%$ ) are: cutaneous adverse reactions (including rash, pruritus, and nail changes), headache, diarrhea, and infection. Refer to the package insert for a complete list of toxicities.

Drug Interactions: No known drug interactions with cetuximab.

## **13. Data Collection and Records to be Kept**

### **13.1 Case Report Forms**

A subset of the National Cancer Institute (NCI) CRFs, in electronic format, will be utilized. Completion of the electronic CRFs (eCRFs) will be done in accordance with the instructions in a study specific data capture plan. All eCRFs will be completed by clinical research coordinators of the OHRS. The eCRFs will be maintained in a confidential format in a secure database.

### **13.2 Data Submission Timeline and Forms**

Completion of eCRFs will occur in accordance with NCI guidelines. Baseline (pre-study) eCRFs (e.g., enrollment, medical history, concomitant medications, disease assessment, etc.) will be completed no later than 14 days after the start of treatment. Treatment eCRFs (e.g., drug administration, adverse events, chemistries, etc.) will be completed no later than 14 days following each cycle of treatment. Off-treatment information (e.g., follow-up, best response, etc.) will be completed no later than 14 days after the end of protocol treatment.

### **13.3 Research Charts**

A research chart (i.e., shadow chart) is maintained at OHRS for each patient enrolled. Copies of significant study source documents will be maintained in the research chart. Examples of source document copies that will be maintained in the research chart include: signed informed consent form, documents that verify eligibility and treatment and documents that verify Grade 3-4 adverse events and response. This information will be updated on a prospective basis and will be confidentially maintained at the OHRS.

### **13.4 Reports**

Publications and annual reports for submission to the IRB will be written by the Rutgers Cancer Institute of New Jersey PI using the data captured on the e-CRFs.

## **14. Data and Safety Monitoring**

Monitoring of this study will occur in accordance with the Cancer Institute's NCI approved Data and Safety Monitoring Plan (DSMP). An "initiation audit" will be conducted in accordance with the DSMP following enrollment of the first two (2) or three (3) patients. Subsequent audits will occur on an annual basis prior to annual IRB continuing review, if the findings from the initiation audit were satisfactory. More frequent audits of patient data and study conduct will occur if necessary. Prior audit findings and/or situations that may arise during the course of the study will determine the need for more frequent auditing. All audit findings will be reported to the Cancer Institute's Human Research Oversight Committee and the PI.

## **15. Statistical Considerations**

### **15.1 Primary Hypothesis**

We hypothesize that the response rate to cetuximab is greater than 10%.

### **15.2 Sample Size Justification**

Sample size was justified based on the primary hypothesis. We expect the response rate is 30%. With 20 patients, the one-sided Binomial exact test at a significance level 0.05 (actual Type I error = 4.32%) will achieve 76.2% power when true response rate is 30%.

### **15.3 Methods for Randomization and Stratification**

This is a safety/feasibility study. There will be no randomization.

### **15.4 Outcome Measures**

The primary outcome is the response rate of cetuximab by RECIST criteria in patients with advanced SCCS.

The secondary outcomes include time to progression, time to death of patients with advanced SCCS who receive neoadjuvant cetuximab. Molecular correlates and tumor size will be also obtained.

### **15.5 Statistical Analysis**

A one-sided Binomial exact test will be used to test the primary hypothesis. The estimation of progression-free survival and overall survival will be performed by the Kaplan-Meier product limit method. Descriptive statistics for all outcome measures will be provided. To evaluate the association between variables, either chi-square test (categorical vs. categorical) or two sample t-test (categorical vs. continuous) or correlation (continuous vs. continuous) will be used depending upon the types of variables in comparison.

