### **1.2 Secondary Objective(s)**

1.2.1 To measure the progression free and overall survival of patients with advanced SCCS who receive neoadjuvant cetuximab.

1.2.3 To determine the conversion to resectability of patients treated with neoadjuvant cetuximab and capture changes in reconstructive options rendered possible by neoadjuvant treatment.

1.2.3 Molecular correlates. All patients must have a biopsy of the locoregional disease (primary site or neck lymph nodes), and of the skin prior to therapy. Patients will also have tissue harvested at surgery that will undergo molecular analysis, or a second post treatment biopsy if surgery is not feasible. Our goals in the molecular analysis are to explore the following possibilities:

- Analyze the relationship of known DNA mutations in tumor per the FoundationOneTM genomic profile, and correlate to clinical endpoints such as clinical benefit and conversion to resectability to discover potential markers of response and/or resistance.
- Measure the downstream activation of signaling pathways without a known driver, including the EGFR pathway.
- Determine if tumor shrinkage with cetuximab is associated with increased apoptosis as evidenced by activated caspase-3, in pre- and post- treatment tumor tissues.
- Determine whether cetuximab results in increased ADCC in post-, compared with pre-treatment tumor tissues.

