### 4. Experimental Design and Methods

#### 4.1 Duration of Study

20 patients are planned to be enrolled. The patients will be under active treatment with cetuximab monotherapy for approximately 8 weeks. Afterwards, they will be assessed for disease response and determination of whether the lesion is potentially resectable will be made. We expect that patients will be accrued within 24 months and that followup time will average 18-24 months per patient.

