## **11. Laboratory Evaluations and Procedures/Correlative and Pharmacokinetic Studies**

### **11.1 An overview of the possible molecular investigations, and in order of priority include**

1. FoundationOne genomic profile from paraffin embedded tumor samples taken before cetuximab, before/at definitive local treatment and after progression
2. Analysis of ADCC and caspase by IHC
3. RNA sequencing of tumor samples before and after cetuximab
4. RNA sequencing of skin samples before and after cetuximab
5. DNA sequencing of tumor and skin samples before and after cetuximab
6. IHC analysis of EGFR downstream pathways that are illuminated by the above

The laboratory investigations are very comprehensive, ranging from partial DNA sequencing (FoundationOne™) in order to check for a battery of known DNA mutations related to cancer, to RNA sequencing on fresh tissue, which will shed light on how protein production is altered when the tumor is treated with cetuximab. FoundationOne™ is targeted DNA sequencing that is performed on paraffin embedded tumor samples. As a pan-cancer test, FoundationOne™ is designed to interrogate the entire coding sequence of 236 cancer-related genes (3,769 exons) plus 47 introns from 19 genes often rearranged or altered in cancer. These genes are known to be somatically altered in human solid cancers based on recent scientific and clinical literature. ADCC and caspase will be examined

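### Section 15.5 names the chi-square test for every categorical association, but with 20 patients its large-sample condition almost never holds; Fisher's exact test is a cheap replacement

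*Combined protocol and SAP*

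**What the plan says.** Section 4.1 sets the size of the study: "20 patients are planned to be enrolled". Section 15.5 then gives one generic rule for all associations, chosen by variable type: "To evaluate the association between variables, either chi-square test (categorical vs. categorical) or two sample t-test", with correlation for two continuous variables. It does not say whether chi-square is used with or without a continuity correction. It names no exact test for sparse tables and no significance level for these comparisons.

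The main foreseeable use of the categorical rule is in the molecular correlates. Section 1.2 plans to take mutations from the genomic profile and "correlate to clinical endpoints such as clinical benefit and conversion to resectability to discover potential markers of response and/or resistance". Section 11.1 describes the assay as "designed to interrogate the entire coding sequence of 236 cancer-related genes (3,769 exons) plus 47 introns from 19 genes". Sections 1.2 and 2.1 present this work as exploratory and preliminary, with validation left to later trials.

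For the primary endpoint the plan already uses an exact method. Section 15.2 states that "the one-sided Binomial exact test at a significance level 0.05 (actual Type I error = 4.32%) will achieve 76.2% power" at a true response rate of 30%.

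**The concern.** Pearson's chi-square test relies on a large-sample approximation, and the usual check is that every expected cell count is at least 5. A mutated/not-mutated by yes/no table in 20 patients will rarely pass. When it fails, the p-value can sit well away from the exact one, and the direction depends on the margins.

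At stake is how far the marker results can be trusted. A gene may be called associated with benefit on a table that an exact test would not call significant. If many genes are examined and the report does not say how many, a reader cannot judge how many such findings chance alone would produce. Section 2.1 hopes the results will inform later patient selection, so a misleading p-value could steer follow-up work to the wrong gene.

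**Working it through.** **Inputs from the documents.** 20 patients (section 4.1); null response rate 10% (section 15.1: "We hypothesize that the response rate to cetuximab is greater than 10"%) and expected rate 30% (section 15.2: "We expect the response rate is 30"%), so about 0.30 × 20 = 6 responders; 236 genes on the panel (section 11.1).

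**Assumptions.** Association tests are two-sided at 0.05. Section 1.2 names clinical benefit and conversion to resectability as endpoints, and the plan assumes no rate for either, so 6/14 and 10/10 splits serve as illustrations. A 14/6 split gives the same results as 6/14.

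**Step 1. The plan's own figure.** Rejecting at 5 or more responses of 20: P(X ≥ 5 | 0.10) = 0.0432 and P(X ≥ 5 | 0.30) = 0.762. Both stated figures reproduce.

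**Step 2. Expected counts.** With m mutated patients and R responders, the smallest expected cell is min(m, 20 − m) × min(R, 20 − R) / 20.
- It reaches 5 only at m = R = 10: 10 × 10 / 20 = 5. That is one of the 19 × 19 = 361 possible margin pairs.
- With R = 6 it runs from 1 × 6 / 20 = 0.3 to 10 × 6 / 20 = 3.0, so no table qualifies.

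**Step 3. One table in full.** Two mutated patients, both among 6 responders (cells 2, 0, 4, 14).
- Uncorrected: 20 × (2 × 14 − 0 × 4)² / (2 × 18 × 6 × 14) = 15,680 / 3,024 = 5.19, p = 0.023.
- Continuity-corrected: 20 × (28 − 10)² / 3,024 = 2.14, p = 0.143.
- Fisher: C(6,2) / C(20,2) = 15 / 190, p = 0.079.

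Two more tables, in the order uncorrected, corrected, Fisher:
- 4 mutated, 3 of them among 6 responders: 0.028, 0.113, 0.061.
- 4 mutated, all on one side of a 10/10 split: 0.025, 0.094, 0.087.

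**Step 4. True size at nominal 5%.** With the margins fixed, this is the sum of the hypergeometric probabilities of all tables with p ≤ 0.05. Values of m above 10 mirror those below.

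| m | R = 6: uncorrected | R = 6: Fisher | R = 10: uncorrected | R = 10: Fisher |
|---|---|---|---|---|
| 1 | 0% | 0% | 0% | 0% |
| 2 | 7.9% | 0% | 0% | 0% |
| 3 | 1.8% | 1.8% | 0% | 0% |
| 4 | 6.1% | 0.3% | 8.7% | 0% |
| 5 | 1.4% | 1.4% | 3.3% | 3.3% |
| 6 | 3.7% | 3.7% | 1.1% | 1.1% |
| 7 | 5.2% | 0.7% | 5.7% | 0.3% |
| 8 | 4.2% | 4.2% | 2.0% | 2.0% |
| 9 | 5.0% | 5.0% | 7.0% | 0.6% |
| 10 | 1.1% | 1.1% | 2.3% | 2.3% |

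The uncorrected test exceeds 5% in 6 of the 20 tables (m = 2, 4, 7 at R = 6; m = 4, 7, 9 at R = 10) and matches Fisher's size in the other 14. The entry at R = 6, m = 9 is 4.98%, just under the level. The continuity-corrected test never exceeds 3.3% in this grid. Other margins can be worse for the uncorrected test: with 4 responders and one mutated patient who responds, the statistic is 20 × 16² / (1 × 19 × 4 × 16) = 4.21, p = 0.040, while Fisher gives 4/20 = 0.20. The size there is 20%.

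**Step 5. Number of chance findings.** If all 236 genes were tested at exactly 5%, the figure would be 236 × 0.05 = 11.8 per endpoint. A gene altered in no patient yields no test, and one altered in a single patient has size 0% at R = 6 or 10. Under assumed skewed mutation prevalences (mean 2% to 20%, R = 6), the expected number per endpoint is 1.3 to 5.9 with uncorrected chi-square and 0.1 to 2.5 with Fisher. The documents give no prevalences, so these figures only show how far the answer moves.

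**The case against.** The strongest reply has four parts.

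- **The inflation is not general.** The three tables in step 3 are among the worst margins. In 14 of the 20 tables uncorrected chi-square has the same size as Fisher. This stands, and it is why the error is described as erratic rather than inflated.
- **The form of the test is unspecified.** With a continuity correction all three examples become non-significant, and the test is conservative. This also stands. It does not rescue the plan, because section 15.5 does not say which form applies and the two can give opposite answers on the same table.
- **Nobody has committed to 236 tests.** A reader might infer that the plan tests every panel gene at 5% and that about 12 false markers per endpoint, or 24 over two endpoints, will be reported. The documents do not support that. Section 15.5 does not mention genes, section 11.1 describes a commercial assay rather than a list of tests, and section 2.1 singles out only TP53, CDKN2A and RAS as known alterations. About 12 is a near-upper figure under assumed full-panel testing, not an expectation.
- **The work is already labelled exploratory.** Sections 1.2 and 2.1 say so and place validation in future trials. That stands, and it makes formal multiplicity adjustment in a 20-patient pilot a matter of choice. It does not justify a test whose approximation fails when an exact one costs nothing more.

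**Conclusion.** The point holds as a cheap improvement. Chi-square is the only method named for categorical pairs, and its expected-count condition is met in one of 361 margin pairs and in none at the planned 6/14 split. Depending on the table and the form of the test, the plan's p-value may be too small or too large. Uncorrected, the size runs from 0% to 8.7% with 6 or 10 responders; corrected, it stays at or below 3.3% in the same grid.

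Applying section 15.5 to the mutation analyses is an inference, but a direct one, since it is the only association rule in the plan. The size figures assume a two-sided 0.05 level and fixed margins. Any count of chance markers would also need mutation prevalences and a list of genes to be tested, and the documents give neither. Only an exploratory part of a secondary objective is affected. The primary exact binomial test and the sample size stay as they are.

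**What to change.** In section 15.5, replace the chi-square test with Fisher's exact test for categorical-by-categorical associations. This matches the exact approach already used for the primary endpoint.

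For the exploratory mutation analyses, add a sentence requiring the report to state how many genes were tested against each endpoint, so that chance findings can be judged. False-discovery-rate-adjusted p-values may be added but are optional.

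The cost is a few words in the plan and trivial programming, with no effect on patients, sample size or conduct. The downside is that Fisher's test is conservative at this size, so fewer associations will be called significant. With 6 responders, a gene mutated in two patients cannot reach p < 0.05 at all, because its smallest attainable p-value is 0.079.

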## **16. Human Subjects**

### **16.1 Subject Population**

The study population for this protocol is advanced squamous cell carcinoma of skin as defined in the eligibility criteria.

### **16.2 Potential Risks**

Potential risks to the patient secondary to cetuximab include the potential for hypersensitivity reaction, rash, hypomagnesemia, and pulmonary complications. These will be monitored as detailed in Sections 7.3.3. In terms of the individual's cancer, there is a risk of treatment not being effective. Furthermore, if the drug is not effective, there is the possibility of disease progression.

### **16.3 Consent Procedures**

Informed consent must be obtained prior to commencing any research procedures. The PI shall seek such consent only under such circumstances that provide the prospective patient opportunity to consider whether or not to participate and that minimizes the possibility of coercion or undue influence. The information given to the patient, or the representative, shall be in a language understandable to the subject or representative. The informed consent document may not include any exculpatory language through which the subject or representative is made to waive any of the subject's legal rights or releases, or appears to release the investigator, the sponsor or the institution from liability for negligence.

### **16.4 Potential Benefits**

The benefits of participating in this study may be improvement in a patient's cancer either as a measure of disease activity or quality of life improvements.

### **16.5 Risk-Benefit Ratio**

All risks and benefits of this treatment will be discussed with the patient prior to enrollment on this study. Along these lines, the basic principles of what we are hoping to accomplish with cetuximab followed by surgery will be explained. The potential risks detailed in Section 16.2 will be made clear as well, along with what measures are in place to minimize these risks.

Alternative treatment will also be discussed. These options include beginning standard chemotherapy if applicable, therapy, monitoring off therapy, or enrolling in another clinical trial. Additionally, the importance of the knowledge gained through this study will be discussed with the patient.

All told, with the combination of employing proper patient selection and study termination criteria, close clinical and lab follow-up (both of the cancer as well as other relevant body systems), and with the medical knowledge of cetuximab (as an FDA-approved medication, for oncologic medical purposes in head and neck and colon cancer) we believe that the potential benefits outweigh the risks of the trial..

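### Section 16.5 relies on study termination criteria, but the protocol text contains no study-level criterion; one non-binding futility look would supply one for efficacy, though not for safety

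*Combined protocol and SAP*

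**What the plan says.** Section 16.5 names "employing proper patient selection and study termination criteria" among the grounds for a favourable risk-benefit judgement, and gives no cross-reference. It also says that patients will be told which measures limit the risks.

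The sections where a study-level rule could be expected read as follows:

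- **Section 4.1:** "20 patients are planned to be enrolled". Accrual is expected to take 24 months.
- **Section 10:** items a to e are reasons for one patient to stop treatment or leave the study.
- **Section 14:** monitoring follows the institution's data and safety monitoring plan. What is described is audits: one after the first two or three patients, then annual ones. "More frequent audits of patient data and study conduct will occur if necessary". No boundary or pause rule is given.
- **Section 15.5:** "A one-sided Binomial exact test will be used to test the primary hypothesis". No interim look is mentioned.
- **Section 1.1:** safety and feasibility are co-primary with response, but no threshold is attached to them.

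**The concern.** A safeguard used to justify the risk, and to be explained to patients, should be one that a reader can find. Here the reader looks in Sections 10, 14 and 15 and finds nothing that would end the study.

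The gap matters in this population. Section 1 describes the disease as potentially resectable (and elsewhere as unresectable), and Section 5.1.1 admits untreated tumours of 2 cm or more. The decision on local treatment follows about 8 weeks of cetuximab, and Section 16.2 lists progression as a risk if the drug does not work. If cetuximab were inactive here, the written plan would still enrol all 20 patients, whatever the first half showed.

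**Working it through.** **Inputs.** From Sections 15.1, 15.2 and 4.1: null response rate 10%, expected rate 30%, N = 20, one-sided exact binomial test at 0.05, 20 patients in 24 months. From Sections 6 and 7.2.3.1: response is read by CT after 8 weeks of treatment (Week 9).

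**1. Reproduce the plan's figures.** Rejecting at 5 or more responses of 20:

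- P(X ≥ 5) at 10% = 0.0432; Section 15.2 states 4.32%.
- P(X ≥ 5) at 30% = 0.7625; Section 15.2 states 76.2%.
- Rejecting at 4 or more would give a type I error of 0.133, so 5 is the lowest valid cutoff.

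**2. Add the look: stop if 0 of the first 10 respond, otherwise go to 20 and reject at 5 or more.** P(stop) = (1 − p)^10:

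| True rate | P(stop) |
|---|---|
| 5% | 0.95^10 = 0.599 |
| 10% | 0.90^10 = 0.349 |
| 30% | 0.70^10 = 0.028 |

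The only rejections lost are those with no response in the first 10 and at least 5 in the second 10. So P(reject) = P(X ≥ 5 of 20) − (1 − p)^10 × P(X ≥ 5 of 10).

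- At 30%: 0.7625 − 0.0282 × 0.1503 = 0.7582. The loss is 0.4 points of power.
- At 10%: 0.0432 − 0.3487 × 0.0016 = 0.0426.

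If the look is overruled, the design reverts to the single-stage test, so type I error is at most 4.32%.

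**3. Expected enrolment at a true rate of 10%.**

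- Accrual paused for the readout: 20 − 10 × 0.3487 = 16.5.
- No pause: 20/24 = 0.833 patients a month; 9 weeks / 4.345 weeks per month = 2.07 months; 0.833 × 2.07 ≈ 1.73 patients enter while waiting. Expected enrolment is 20 − 0.3487 × (10 − 1.73) = 17.1.

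The average saving is therefore 3.5 patients with a pause and 2.9 without. In a trial that stops, it is 10 or about 8.

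**4. Other looks, with N = 20 and the cutoff of 5 kept.** Expected enrolment assumes a pause.

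| Stop if | P(stop) at 10% | Power | Expected N at 10% |
|---|---|---|---|
| 0 of 10 | 34.9% | 75.8% | 16.5 |
| ≤ 1 of 13 | 62.1% | 75.5% | 15.7 |
| ≤ 1 of 10 | 73.6% | 71.6% | 12.6 |

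The low cost belongs to the named rule. Stopping at 1 or fewer of 10 costs 4.7 points of power.

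**5. Patients who cannot be assessed.** Section 5.1 does not require CT-measurable disease, while Section 9.2 uses no lesion below 10 mm. As an assumption for illustration: if 2 or 3 of the first 10 could not be assessed and counted as non-responders, the chance of wrongly stopping at a true 30% among the rest would be 0.7^8 = 5.8% or 0.7^7 = 8.2%, instead of 2.8%. Hence the look should wait for 10 assessable patients.

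**6. Information given up on stopping.** With no events of a given kind, the one-sided 95% upper bound is 1 − 0.05^(1/n): 25.9% at n = 10 and 13.9% at n = 20.

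**The case against.** A single-stage pilot of 20 patients is a legitimate design, and the test in Section 15.2 is sound. Section 16.5 may be using loose words for Sections 5 and 10, since it pairs patient selection with termination and concerns what is discussed with each patient. On that reading a cross-reference would be enough. Exposure is also limited patient by patient: Section 6 schedules weekly examination and tumour-site assessment, and item d of Section 10 allows the investigator to stop treatment.

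Much of this stands. It makes the look an improvement rather than a necessity, and it does not support the inference that every patient must complete 8 weeks whatever happens. It does not put a study-level criterion into the plan.

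A reader might also infer that no termination criteria exist at all. The documents do not support that: the monitoring plan named in Section 14 was not supplied and may hold powers to suspend the study. The supportable statement is that none appears in the protocol text.

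Three limits on the benefit also stand. At exactly 10%, the rule of 0 of 10 lets the trial continue about 65% of the time. Stopping early leaves fewer patients for the safety and molecular data. And Section 14 describes its oversight committee only as receiving audit findings, so the plan does not show that it would review response data.

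**Conclusion.** The point holds in a limited form. Section 16.5 relies on study-level termination criteria that cannot be found in the protocol text, and accrual would reach 20 even after no responses in the first 10. A futility look can fill part of the gap for about 0.4 points of power, with no increase in type I error. Its saving at a true rate of 10% is moderate: about 3 patients on average, with or without a pause.

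These figures assume that all 20 patients are assessable, that the final cutoff stays at 5, and that accrual follows the planned 20 in 24 months. If some patients are not assessable, the tenth assessable readout comes later and the saving shrinks.

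It would be tempting to conclude that the look makes good the risk argument in Section 16.5. It does not. It acts only on lack of response, and safety, although co-primary, would still have no study-level criterion in the text.

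**What to change.** 1. **Sections 15.2 and 15.5.** Add one non-binding futility look once the first 10 response-assessable patients have had the post-treatment CT. Stop accrual if there is no complete or partial response; otherwise continue to 20 and reject at 5 or more. Define who counts as assessable and state the operating characteristics above. Stopping at 1 or fewer of 13 is a reasonable alternative if a higher chance of stopping an inactive regimen is wanted. The rule concerns accrual only, not the treatment of patients already enrolled.
2. **Accrual during the readout.** State whether it pauses, and quote the matching expected enrolment: 16.5 with a pause, about 17.1 without.
3. **Section 14.** Name who receives the look. If it is the existing oversight committee, say that its remit includes this report.
4. **Section 16.5.** Cite the new rule and any suspension provision of the monitoring plan that the argument relies on. Describe the look as a futility rule. If no study-level safety criterion exists, do not imply one.

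**Cost:** about 0.4 points of power (0.7 for the alternative), one short report, and a smaller safety and correlative dataset in trials that stop. No added patients are needed, and the CT is already scheduled. A pause, if chosen, would hold accrual for roughly 9 weeks.
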